**Schematic of Study Design**

1. Lesions must not be in a hair-bearing area on the scalp, in the mouth, on the lips, genitalia, nails, around/on the eyes, inside ear.
2. All lesions of all subjects will be evaluated by teledermatologist team. If at least one of three possible lesions was not recommended for biopsy by the in-person dermatologist, this subject will receive a telemedicine consensus recommendation report to (or not to) biopsy within 3 business days of participant evaluation. If all eligible lesions were recommended for biopsy by the in-person dermatologist, this subject will not receive the telemedicine evaluation report.
3. The following lesions will have clinical and dermoscopic image taken, but will not have a Nevisense score: Lesions on an acral site, lesions with recurrence after biopsy/excision, lesions in a scar, lesions with foreign material (e.g. tattoo, splinter, etc), lesions in an area of active sunburn, lesions on a stalk, lesions with crust. Bleeding or ulcerated lesions are will only have a clinical image taken (no dermoscopic or Nevisense score).
4. Current gold standard evaluation for skin lesion of concern. For subjects with more than 1 lesion evaluated, they may have 1 or more recommended for biopsy by the in-person dermatologist (or equally 1 or more recommended for no biopsy by the in-person dermatologist).

**Telemedicine Team Clinical Decision-Making Algorithm**

\*Teledermatologist will be given Nevisense data to assess impact of Nevisense score on decision to biopsy, however, if imaging concerning for malignancy, biopsy will always be recommended given that this device is being used in an investigational setting.

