The long-term goal of this project is to reduce poor melanoma outcomes among underserved communities by delivering state-of-the-art diagnostic expertise to these neighborhoods via telemedicine. In the proposed pilot study, we plan to model a walk-in clinic, like the CVS Minute Clinic, in the NYU Dermatology Clinical Studies Unit (DCSU). We will test the effectiveness of an enhanced teledermatology service to accurately evaluate up to 3 self-identified skin lesions of concern per member of the general public. In addition to obtaining clinical and dermoscopic images of the skin lesions, we will enhance the evaluation with a Nevisense device. Nevisense, which uses a small hand-held probe and electrical impedance spectroscopy (EIS), received FDA clearance (PMA) in 2017 "for use on cutaneous lesions with one or more clinical or historical characteristics of melanoma, when a dermatologist chooses to obtain additional information when considering biopsy". The validation study showed a sensitivity of 97% and specificity of 34% for the diagnosis of melanoma. The negative predictive value, important for a screening tool, was 98%. Importantly, the lesions in this study were preselected by dermatologists. It is known that Nevisense can deliver false positive results for common benign skin lesions that are likely to be encountered frequently in a walk-in clinic setting. These lesions are easily diagnosed using teledermoscopy, so we will investigate whether the combined dermoscopic and Nevisense evaluation will have a higher sensitivity and specificity than either technique alone, and will be comparable to, or potentially more accurate than, an in-person evaluation by a clinical dermatologist. A similar service is available in Norway through ScreenCancer ([www.screencancer.com](http://www.screencancer.com)). The Norwegian pharmacies use a dermatologist review of computer-enhanced dermoscopy images without Nevisense. Between 2010-2014, they conducted 25,836 scans in 109 pharmacies, recommended biopsies of 8% of lesions, and diagnosed 154 melanomas. In 2014, they diagnosed 4% of all Norwegian melanoma cases. These results demonstrate the potential of our SpotCheck platform to improve the outcomes of melanoma patients, especially those with fair skin residing in medically underserved communities.

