### **2.3 Rationale**

Detection of melanoma at its earliest stages is associated with high surgical cure rates, without the need for additional, potentially toxic and expensive systemic therapies. Rural and other medically underserved communities have higher rates of melanoma mortality that is associated with reduced access to dermatologic diagnostic services. We aim to study the effectiveness of an augmented telemedicine diagnostic platform for melanoma and other skin cancers that can potentially be deployed in pharmacies and urgent care centers that would be more available in rural communities than dermatologist offices.

The study will evaluate participant-selected lesions of adults in the New York City metropolitan area to simulate the walk-in clinic or pharmacy community setting. The control is an in-person evaluation by a community dermatologist, the current gold

standard. We aim to assess the sensitivity and specificity of the platform compared to the in-person dermatological examination in the diagnosis of melanoma and other skin cancers. Since the Nevisense evaluation is one component of the platform, and the current FDA approval is for it to be used in dermatologist offices to aid in biopsy decisions, we will also examine the degree to which teledermatologists can use the clinical and dermoscopy images to evaluate whether each study lesion would have been appropriate for the Nevisense evaluation had they seen the patient in-person. Finally, we will examine whether the combined teledermoscopy/clinical images plus Nevisense will have greater sensitivity and specificity to diagnose melanoma and other skin cancers than either approach alone.

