In addition to the DermLite Cam images, a study specific camera or EPIC HAIKU will be used to acquire 3 clinical images of <5 seconds per lesion (from 6 inches away, 12 inches away, and 18 inches away). Images will be stored in the patient's medical record in Epic, to which the teledermatology team has access. Clinical images taken through Epic Haiku or the study specific camera will not be stored elsewhere. Images taken with the study specific camera will be deleted from the camera once images are uploaded to EPIC.

The Barco Demetra device will be used to acquire 3 images of <5 seconds per lesion (one clinical, one polarized dermoscopic, and one non-polarized dermoscopic) as well as 3 additional clinical images of <5 seconds per lesion (from 6 inches away, 12 inches away, and 18 inches away). Images will be stored in the authenticated and data-encrypted Demetra Cloud accessible via the web by the telemedicine team in the NYU Department of Dermatology Pigmented Lesion Clinic. The telemedicine dermatology team will review the images using this dedicated cloud software. Clinical and dermoscopic images taken by the Barco Demetra device will not be stored elsewhere.

Lesions with bleeding or ulceration will only have a clinical image taken and not have a dermoscopic image taken.

The telemedicine dermatology team will consist of [name], [name], and [name], who are all pigmented lesion experts. They will be listed as co-investigators. They will submit independent, blinded to each other, diagnoses for each lesion on REDCap. If at least one teledermatologist believes the lesion to be a malignant diagnosis, the lesion will be recommended for biopsy. If the participant has not already had the lesion biopsied by the in-person recommendation, the participant will be told this concern for malignancy and telemedicine recommendation for biopsy.

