#### 10.3.2 Analysis of the Primary Efficacy Endpoint(s)

To determine the agreement between in-person recommendation and the telemedicine (tele) recommendation we can calculate the number of discordant benign vs. malignant diagnoses; specifically, the number of subjects that were recommended a biopsy from the in-person dermatologist but were recommended no biopsy from the teledermatology team, and the number of subjects that were recommended no biopsy from the in-person dermatologist but biopsy by the teledermatologist team. We can calculate the Kappa coefficient as a measure of the degree of concordance or agreement with confidence intervals. We can also calculate "sensitivity" and "specificity" of the tele method assuming in-person diagnosis as the gold standard. Similarly, we can separately evaluate the agreement between in-person and: 1) dermoscopy alone; and 2) Nevisense (EIS score  $\geq 4$ ) without dermoscopy. We will also estimate the improvement (if any) of using both methods compared to one method. We expect the Kappa coefficient to be close to one, and high "sensitivity" and "specificity" (close to 1) for the SpotCheck method assuming in-person diagnosis as the gold standard.

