#### 10.3.3 Analysis of the Secondary Endpoint(s)

Secondary endpoint (1) will be a descriptive analysis of Sensitivity, Specificity, Positive Predictive Value, and Negative Predictive Value, using the histopathology results as the gold standard. We will assess potential difference or advantages in terms of: a) enhanced telemedicine diagnostic system; b) telemedicine Nevisense alone; c) telemedicine clinical + dermoscopy alone; and d) in-person dermatologist diagnosis. Sensitivity, Specificity, Positive Predictive Value, and Negative Predictive Value will be reported with an upper and lower confidence interval. Lesions with missing data will not be included in the relevant analyses (see Study Design schematic footnote 3). Participants lost to follow-up for reporting his/her biopsy results will be included in the analysis as the data required for analysis has been collected.

As another secondary endpoint, we will be evaluating the enhanced telemedicine service's impact on patient centered outcomes. Descriptive statistics for this secondary endpoint (2) (patient questionnaires, Supplement L will be presented as percentages. Study completion questionnaires may be qualitatively analyzed for themes and quantified by thematic representation across participants. Participant agreement of thematic categories will be calculated as percentages as a summary measure. Factors for stratification may include participants with a biopsy procedure and those without biopsy procedure as well as diagnosis of malignancy or benign lesion within those with biopsy. Participants with missing study completion questionnaire results due to inadequate duration of phone call will not be included.

As a final secondary endpoint (3), we will estimate the number of lesions that may benefit from the additional information of the Nevisense score to the clinical and dermoscopic exam. This estimation will be provided by the in-person dermatologist, and separately by each of the three teledermatologists (Supplement T & U). The estimates will be expressed as percentages. Any lesion with missing data in the in-person dermatologist and teledermatologist plan will not be included in analysis. Participants lost to follow-up will still be included in analysis of this endpoint as required data for this endpoint determination has been captured in the first visit.

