**10.3.11 Exploratory Analyses**

Exploratory analysis may be conducted using the continuous Nevisense score or categorical unequivocally benign lesion designation (using clinical and dermoscopic image alone) as factors of stratification before re-evaluation of primary endpoint again.

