## **10.5 Measures to Minimize Bias**

### **10.5.1 Enrollment/Randomization/Masking Procedures**

**10.5.2** Subjects will be self-enrolled into the study by viewing an advertisement and making an appointment for enrollment at the DCSU. Enrollment procedures include eligibility verification and informed consent confirmation with signature. The in-person dermatologist (control arm) and telemedicine team (intervention arm) will each be blinded to the other's management recommendation. The in-person dermatologist will be blinded to the Nevisense score. Additionally, the teledermatologist team of 3 physicians will be masked to each other's management plan. If one teledermatologist is absent (due to vacation, illness etc.) and cannot make their recommendations, a minimum of 2 teledermatologists is satisfactory to make a consensus. If any teledermatologist recommends biopsy, the team recommendation will be biopsy. Periodic reviews of teledermatology diagnoses by the teledermatology team will be held in order to improve quality control during the study. **Evaluation of Success of Blinding**

Not applicable

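### On the same lesions and reads, if imaging alone counts 'concerning' as positive, adding Nevisense cannot raise specificity above imaging alone; the available text neither states that threshold nor fixes a common lesion set

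*Combined protocol and SAP*

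**What the plan says.** The footnote to the Telemedicine Team Clinical Decision-Making Algorithm gives the readers the Nevisense score but adds that "if imaging concerning for malignancy, biopsy will always be recommended given that this device is being used in an investigational setting". Two sections apply an any-reader rule at team level. Section 6.1.4 says "If at least one teledermatologist believes the lesion to be a malignant diagnosis, the lesion will be recommended for biopsy", and section 10.5.1 says "If any teledermatologist recommends biopsy, the team recommendation will be biopsy".

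The question about combining methods is put twice. Section 2.1 will investigate whether the combined evaluation "will have a higher sensitivity and specificity than either technique alone". Section 2.3 will examine whether clinical and dermoscopic images "plus Nevisense will have greater sensitivity and specificity to diagnose melanoma and other skin cancers than either approach alone". The matching analyses are in section 10.3.2, "We will also estimate the improvement (if any) of using both methods compared to one method", and in section 10.3.3, which uses histopathology as the reference: "We will assess potential difference or advantages in terms of: a) enhanced telemedicine diagnostic system", followed by b) Nevisense alone, c) clinical images plus dermoscopy alone, and d) the in-person dermatologist.

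Section 10.3.2 gives Nevisense alone a cut-off, a score of 4 or more. For an image-only call, section 10.3.11 names, as an exploratory stratifier, a "categorical unequivocally benign lesion designation (using clinical and dermoscopic image alone").

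Section 10.2 sets one general dataset: eligible lesions assessed by both sides. Section 10.3.3 then removes lesions with missing data from whichever analyses they affect. It refers to footnote 3 of the study schematic, which lists lesions that get no score and some that get no dermoscopy.

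**The concern.** If the decision rule itself fixes which way specificity can move, the comparison of a) with c) cannot answer the specificity half of the question in sections 2.1 and 2.3, however well the device performs. Whether that is so depends on what counts as a positive image under c).

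The second issue is case mix. If a) is computed on scored lesions and c) on all imaged lesions, the difference between them mixes the effect of the score with the difference between scored and unscored lesions. A reader could then not tell whether a specificity difference comes from the score, the rule or the lesions. What Nevisense adds to imaging is a stated question of this pilot, so both choices should be settled before the data are analysed.

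**Working it through.** **1. The plan's own counts.** Section 10.4 expects a 10% biopsy rate: 0.10 × 500 = 50 to 0.10 × 1000 = 100 biopsies recommended, and 0.90 × 500 = 450 to 0.90 × 1000 = 900 not. These figures reproduce. The Protocol Summary bases accuracy on biopsied lesions, so 50 to 100 is the working range, treating each recommendation as a biopsy.

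**2. Inclusion.** Suppose a reader's image call is positive under c) when the images are concerning. By the footnote that reader recommends biopsy, and by the any-reader rule so does the team. Every lesion positive on c) is therefore positive on a). With N benign lesions and k of them positive on a) only,

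specificity(a) = specificity(c) − k/N, with k ≥ 0.

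With M cancers and m of them positive on a) only,

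sensitivity(a) = sensitivity(c) + m/M, with m ≥ 0.

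A simulation of 20,000 three-reader data sets under these rules gave no exception. No such nesting holds against b): a benign lesion with a high score and plainly benign images can be positive on b) and negative on a).

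**3. Size of one lesion.** Section 2.4.2 expects 8% of subjects to have a benign biopsy and 2% a malignancy, a ratio of 4:1. Applying this subject-level ratio to lesions is an assumption. Section 14.3 cites 29:1.

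- 4:1: 0.8 × 50 = 40 to 0.8 × 100 = 80 benign; 10 to 20 cancers.
- 29:1: 50 × 29/30 = 48.3 to 100 × 29/30 = 96.7 benign; 1.7 to 3.3 cancers.
- Each benign lesion positive only through the score: 1/97 = 1.0 to 1/40 = 2.5 points of specificity. Five such lesions: 5/97 = 5.2 to 5/40 = 12.5 points.
- Each cancer found only through the score: 1/20 = 5 to 1/10 = 10 points of sensitivity at 4:1.

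**4. The threshold decides the direction.** For illustration, let a share p of benign lesions be concerning on images and a share e be equivocal. Let equivocal lesions follow the score, with Nevisense specificity s. Then specificity(a) = 1 − p − e(1 − s).

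- c) positive means concerning: specificity(c) = 1 − p, so a) − c) = −e(1 − s).
- c) positive means not unequivocally benign: specificity(c) = 1 − p − e, so a) − c) = +e·s.

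With assumed e of 10 to 20%, and s from 34% (the validation figure in section 2.1) to 100%, the first runs from −0.20 × 0.66 = −13.2 points to 0. The second runs from 0.10 × 0.34 = +3.4 to 0.20 × 1.00 = +20.0 points. These are shares of all benign lesions, not only biopsied ones. They show the sign and do not forecast the size.

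**5. Unequal lesion sets.** Let u be the unscored share of benign lesions, d the imaging specificity in scored minus unscored lesions, and L the true loss on the scored lesions. With a) on scored lesions and c) on all, the apparent difference is u·d − L. The documents give none of these inputs. Assuming u up to 30% and d up to 20 points either way:

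- L = 2.5: from 0.3 × (−20) − 2.5 = −8.5 to 0.3 × 20 − 2.5 = +3.5 points.
- L = 5: at most 0.3 × 20 − 5 = +1.0 point.
- L = 6 or more: no apparent gain within these ranges.

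**6. Which lesions are scored.**

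- Section 5.2 bars measurement in areas of psoriasis or eczema; section 6.1.4 says that restriction will not be followed.
- Schematic footnote 3 keeps lesions recurrent after biopsy or excision as imaged but unscored; section 5.2 excludes previously biopsied lesions.
- Sections 2.4.1 and 7.3.2 describe a measurement for each lesion, without the exceptions in footnote 3 and section 5.2.

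**The case against.** The strongest reply is that the algorithm figure and the teledermatologist form (Supplement U) are not available here, and either may state the image threshold. That stands. A reader might infer that the plan has no threshold or records no image-only call, but the documents do not support this. The footnote says the score is shown so that its effect on the biopsy decision can be assessed, and section 10.3.11 names an image-only designation. Both suggest that an image-only call may be recorded.

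A reader might also infer that the lesion sets are undefined. They are not: section 10.2 gives a dataset and section 10.3.3 a missing-data rule. If a) uses imaging alone wherever a score is absent, a) and c) can cover the same lesions and the inclusion still holds. What remains is that the text does not say whether a) does so, or whether unscored lesions also leave c).

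The plan only asks whether the combination is better. Section 10.1 rules out hypothesis testing, and the formal objective in section 3.2 compares with the in-person dermatologist. This limits the weight of the point. It does not help a reader interpret the a) versus c) difference once it is reported.

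The general statements in sections 2.4.1 and 7.3.2 can fairly be read as qualified by the specific exceptions. The other two conflicts cannot be resolved that way.

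**Conclusion.** The point holds conditionally. On the same lesions and reads, and if c) counts concerning images as positive, the design rules out a specificity gain over imaging alone and allows only equal or higher sensitivity. The cost is about 1.0 to 2.5 points of specificity for each benign lesion added by the score, given 40 to 97 benign biopsied lesions.

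The stronger reading, that the combined method can never show better specificity than imaging alone, is not supported. A broader positive class for c) could reverse the sign, and so could unequal lesion sets. The comparison with Nevisense alone stays open. The threshold and unequal-set figures are illustrations resting on assumed inputs, and clustering of lesions within participants is ignored.

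This is a descriptive secondary comparison. The primary agreement between the telemedicine team and the in-person dermatologist is unaffected, although the dermoscopy-alone agreement in section 10.3.2 needs the same threshold.

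**What to change.** Leave the recommendations given to participants unchanged.

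1. In section 10.3.3, compare the methods, in particular a) with b) and with c), as paired results on lesions that have clinical image, dermoscopy and score. Keep a) versus d) on all eligible biopsied lesions as well, since section 3.2 asks for it. Give the counts lacking each component, and say how a) is scored when a component is absent.
2. State the image-positive threshold for c), based on each reader's image-only call made before the score is shown, unless the algorithm figure or Supplement U already does so.
3. If the threshold is concerning for malignancy, say in sections 2.1, 2.3, 10.3.2 and 10.3.3 that against imaging alone the score can only add biopsy recommendations. Report the extra cancers and the extra benign biopsies. If another threshold is chosen, also report benign biopsies spared and cancers missed.
4. Reconcile schematic footnote 3 and sections 2.4.1, 5.2, 6.1.4 and 7.3.2 on which lesions are eligible and which are scored. This review does not say which rule is right.

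The cost is wording, and at most one form field per reader per lesion. Each method's own interval is wider on the common set. If 70 to 90% of lesions have all components (an assumption), the widening factor is about 1/√0.9 = 1.05 to 1/√0.7 = 1.20. The all-lesion results for a) and d) are kept.

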## 2 Introduction, Background Information and Scientific Rationale

### 2.1 Background Information and Relevant Literature

Recognition and diagnosis of early stage melanomas is associated with  $\geq 98\%$  10-year survival for tumors  $< 0.8\text{mm}$  in thickness. In contrast, more advanced stages have 10-year survivals ranging between 94% - 75% for localized disease, and much lower rates for regional and distant metastatic disease. Nearly all patients diagnosed with early stage disease are cured surgically. Besides exhibiting reduced mortality, these patients experience less complicated and less costly care, and will not be exposed to the potential toxicities of the new systemic therapies for advanced disease.

Associations between access to healthcare and cancer health outcomes are well established. In melanoma, several studies reveal that populations with lower socioeconomic levels, decreased physician supply, and increased distance to a diagnosing provider are diagnosed with more advanced stage disease than populations with better access. There is a need to reduce the barriers to access for diagnostic services when patients have a skin lesion of concern, especially in areas of decreased physician supply. In areas with ample physician supply, however, many benign growths are unnecessarily removed out of concern for melanoma because most providers do not use modern technologies to augment their diagnostic skills. Dermoscopy, which is a non-invasive, 10x magnification technique to visualize skin structures and colors not visible to the naked eye, improves diagnostic accuracy and thus decreases ratios of benign-to-malignant biopsy excisions.

Over the last several years, store-and-forward telemedicine technology has advanced, enabling expert diagnostic services to be provided to areas of low physician supply by providing images to providers working remotely. A recent Cochrane Review of store-and-forward teledermoscopy studies noted that these technologies are likely to appropriately triage lesions for in-person assessment by a health care provider.

The long-term goal of this project is to reduce poor melanoma outcomes among underserved communities by delivering state-of-the-art diagnostic expertise to these neighborhoods via telemedicine. In the proposed pilot study, we plan to model a walk-in clinic, like the CVS Minute Clinic, in the NYU Dermatology Clinical Studies Unit (DCSU). We will test the effectiveness of an enhanced teledermatology service to accurately evaluate up to 3 self-identified skin lesions of concern per member of the general public. In addition to obtaining clinical and dermoscopic images of the skin lesions, we will enhance the evaluation with a Nevisense device. Nevisense, which uses a small hand-held probe and electrical impedance spectroscopy (EIS), received FDA clearance (PMA) in 2017 "for use on cutaneous lesions with one or more clinical or historical characteristics of melanoma, when a dermatologist chooses to obtain additional information when considering biopsy". The validation study showed a sensitivity of 97% and specificity of 34% for the diagnosis of melanoma. The negative predictive value, important for a screening tool, was 98%. Importantly, the lesions in this study were preselected by dermatologists. It is known that Nevisense can deliver false positive results for common benign skin lesions that are likely to be encountered frequently in a walk-in clinic setting. These lesions are easily diagnosed using teledermoscopy, so we will investigate whether the combined dermoscopic and Nevisense evaluation will have a higher sensitivity and specificity than either technique alone, and will be comparable to, or potentially more accurate than, an in-person evaluation by a clinical dermatologist. A similar service is available in Norway through ScreenCancer ([www.screencancer.com](http://www.screencancer.com)). The Norwegian pharmacies use a dermatologist review of computer-enhanced dermoscopy images without Nevisense. Between 2010-2014, they conducted 25,836 scans in 109 pharmacies, recommended biopsies of 8% of lesions, and diagnosed 154 melanomas. In 2014, they diagnosed 4% of all Norwegian melanoma cases. These results demonstrate the potential of our SpotCheck platform to improve the outcomes of melanoma patients, especially those with fair skin residing in medically underserved communities.

The overall goal of this research is to develop a platform that can increase patient access to expert skin cancer diagnostic services via telemedicine. This is especially important for medically underserved areas where melanoma outcomes are worse than in areas with greater access to in-person evaluations. If successful, the widespread availability of such services would be combined with public education efforts to encourage individuals with changing skin lesions to seek evaluation. With decreased travel times to high quality diagnostic services, such efforts may decrease the diagnosis of more advanced melanomas (with a concomitant increase in the diagnosis of earlier stage tumors), and potentially decrease melanoma mortality.

